### **7.1.1.2 Other Events of Special Interest**

Other events of special interest (OEOSI) consist of a list of preferred terms grouped by specific category (e.g. Myositis Event, Myocarditis Event, Demyelination Event, Guillain-Barre Syndrome, Pancreatitis Event, Uveitis Event, Encephalitis Event, Myasthenic Syndrome, Rhabdomyolysis Event, Graft Versus Host Disease). The list of MedDRA preferred terms used to identify OEOSI is revisited quarterly and updated accordingly. The preferred terms used for the selection at the time of the database lock by categories will be provided.

### **7.1.1.3 Immune-Mediated Adverse Events (US Submission)**

In order to further characterize AEs of special clinical interest, analysis of immune-mediated AEs (IMAE) will be conducted. IMAEs are specific events (or groups of PTs describing specific events) that include pneumonitis, diarrhea/colitis, hepatitis, nephritis/renal dysfunction, rash, endocrine (adrenal insufficiency, hypothyroidism/thyroiditis, hypothyroidism, thyroiditis, hyperthyroidism, diabetes mellitus, and hypophysitis), and other specific events, considered as potential immune-mediated events by investigator that meet the definition summarized below:

- those occurring within 100 days of the last dose,
- regardless of causality,
- treated with immune-modulating medication (of note, endocrine AEs such as adrenal insufficiency, hypothyroidism/thyroiditis, hypothyroidism, thyroiditis, hyperthyroidism,

diabetes mellitus, and hypophysitis are considered IMAEs regardless of immune-modulating medication use, since endocrine drug reactions are often managed without immune-modulating medication).

- with no clear alternate etiology based on investigator assessment, or with an immune-mediated component.

The list of MedDRA preferred terms used to identify IMAEs is revisited quarterly and updated accordingly. The preferred terms used for the selection at the time of the database lock by categories will be provided.

### **7.1.2 Laboratory Tests**

Clinical laboratory parameters (hematology, serum chemistry and electrolytes) will be evaluated.

Laboratory tests will be graded using the NCI Common Terminology Criteria, and the most recent version of the criteria at the time of the database lock will be used.

Clinical laboratory data will be first analyzed using International System of Units (SI).

Analyses will be repeated using US conventional units if needed.

In the laboratory summary tables, unless otherwise specified, subjects will be counted only once for each lab parameter according to their worst on treatment CTC grade (worst being the highest CTC grade). The laboratory tables and listings will be sorted by laboratory category, laboratory subcategory and laboratory test code sequence number.

## **7.2 Study Conduct**

Unless otherwise specified, the study conduct data will be presented by cohort and all treated subjects (for safety run-in phase), or by treatment arm and all randomized subjects (for randomized phase).

### **7.2.1 Relevant Protocol Deviations**

The following programmable deviations will be considered as relevant protocol deviations and summarized by treatment group and overall in all treated subjects (for safety run-in phase) and in all randomized subjects (for randomized phase). Non-programmable relevant eligibility and on-study protocol deviations, as well as significant (both programmable and non-programmable) eligibility and on-study protocol deviations will be reported through [REDACTED] listings.

#### Eligibility:

- Subjects without measurable disease at baseline as per investigator, or with measurable baseline primary tumor of < 2 cm in largest diameter
- Subjects with unknown or negative ER
- Subjects with unknown or positive HER2

- Subjects received any treatment, including radiotherapy, chemotherapy, and/or targeted therapy, administered for the currently diagnosed BC prior to enrollment.
- Subjects with baseline ECOG performance status > 1
- Subjects with misclassified stratification factor levels (IVRS vs clinical database; for randomized phase only)

On-study:

- Subjects receiving any concurrent anti-cancer therapy (chemotherapy, hormonal therapy, immunotherapy, standard or investigational agents for treatment of cancer) outside of the protocol-specified neoadjuvant therapy while on study.
- Subjects whose “as treated” arm different than their as randomized arm (subjects who received the wrong treatment for the entire neoadjuvant treatment period, excluding the never treated)

### **7.2.2 Accrual**

Enrollment by country and site, and enrollment by month will be summarized and listed for all enrolled subjects.

A by-subject listing of batch numbers for all treated subjects will be provided.

### **7.3 Study Population**

Analyses in this section will be tabulated for all randomized subjects in randomized phase by treatment group as randomized; and for all treated subjects in Safety Run-in phase by cohort group, unless otherwise specified.

#### **7.3.1 Subject Disposition**

The total number of subjects enrolled (randomized or not randomized for randomized phase; treated or not treated for safety run-in phase) will be presented along with the reason for not being randomized/treated. This analysis will be performed on all enrolled subjects population only.

Number of subjects randomized but not treated along with the reason for not being treated will be tabulated by treatment group as randomized in randomized phase.

Number of subjects who discontinued study treatment along with corresponding reason will be tabulated by treatment group as treated. Reason for discontinuation will be derived from subject status CRF page. Number of subjects who did not receive surgery along with corresponding reason will be tabulated by treatment group as treated. Reason for not receiving surgery will be derived from subject status CRF page. This analysis will be performed only on all treated subjects population.

A by-subject listing for all treated subjects will be provided showing the subjects off treatment date, whether the subject continue in the treatment period/study along with the reason for going off treatment period/study, and whether subject received surgery along with the reason for not receiving surgery. A by-subject listing for all enrolled subjects will also be provided, showing whether the subject was randomized/treated along with the reason for not being randomized/treated.

### **7.3.2 Demographics and Other Baseline Disease Characteristics**

The following demographic and baseline disease characteristics will be summarized and listed by treatment group as randomized (in randomized phase) or treatment group as treated (in safety run-in phase):

- Age (continuous)
- Age categorization (< 65, ≥ 65 and < 75, ≥ 75 and < 85, ≥ 85, ≥ 75, ≥ 65)
- Sex (Male vs. Female)
- Race (White, Black or African American, Asian, American Indian or Alaska Native, Native Hawaiian or Other Pacific, Asian Indian, Chinese, Japanese, Malay, Asian Other, Other)
- Ethnicity (Hispanic/Latino and Not Hispanic/Latino)
- Country by geographic region
- ECOG performance status (0, 1, >1)
- Tumor size (> 3 cm or ≤ 3 cm) (randomized phase only)
- Evaluation of lymph nodes (cytologically positive vs radiologically or cytologically negative) (randomized phase only)

Summary table (cross-tabulation) by treatment group for stratification factor (except for region) will be provided to show any discrepancies between what was reported through IRT vs. other data sources at baseline. This summary will be performed based on all randomized subjects (randomized phase only).

A listing of randomization scheme presenting randomized treatment group and as treated treatment group will be provided for all randomized subjects (randomized phase only).

A by-subject listing of FSH level and/or Estradiol level for female participants with age ≤ 55 will be provided to confirm menopause at screening.

### **7.3.3 Medical History**

A by-subject listing of general medical history for all randomized subjects in the randomized phase and for all treated subjects in the Safety Run-in phase will be provided.

### **7.3.4 Prior Therapy Agents**

- Prior cancer therapy will be summarized by treatment group and overall.
- Prior systemic cancer therapy will be summarized by treatment group and overall and listed by subject.
- Prior radiotherapy and prior surgery related to other cancer will be listed by subject.

### **7.3.5 Physical Examinations**

Subjects with abnormal baseline physical examination will be listed by subject.

### **7.3.6 Baseline Physical Measurements**

Baseline physical measurements will be listed by subject.

## 7.4 Extent of Exposure

Listings will include all available exposure data. Analyses will be performed by treatment group “as treated” in all treated subjects, unless otherwise specified.

### 7.4.1 Administration of Study Therapy

The following parameters will be summarized (descriptive statistics) by treatment group (groups are also differentiated by phase: Safety Run-in Phase, Randomized Phase):

- Time from randomization to first dose of study therapy (0 to 3 days, > 3 to 7, >7 to 14, >14 to 21, >21 to 28, >28), for randomized phase only.
- The following parameters will be summarized (descriptive statistics) by study therapy and treatment group:
- Number of doses received (nivolumab, anastrozole, palbociclib and abemaciclib [for participants in cohort 1])
- Cumulative dose
- Relative dose intensity (%) using the following categories: < 50%; 50 - < 70%; 70 - < 90%; 90 - < 110%; ≥ 110%
- Average daily dose

Duration of study therapy will be summarized (descriptive statistics) by treatment group.

A by-subject listing of dosing of study medication (record of study medication, infusion details, and dose changes) will be also provided.

**Table 7.4.1-1: Administration of study therapy: definition of parameters, IV therapy**

Nivolumab	
Dosing schedule per protocol	480 mg every 4 weeks
Dose	Dose (mg) is defined as Total Dose administered (mg). Dose administered in mg at each dosing date and weight are collected on the CRF.
Cumulative dose	Cum dose (mg is sum of the doses (mg) administered to a subject during the treatment period.
Relative dose intensity (%)	$[\text{Cum dose (mg)} / ((\text{Last dose date} - \text{Start dose date} + 28) \times 480 / 28)] \times 100$
Duration of study therapy	Last dose date - Start dose date +1

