8.1.1 Nivolumab Dose Discontinuation

If a participant discontinues nivolumab, the entire study treatment (CDK4/6 inhibitor and anastrozole) must be discontinued.

Nivolumab treatment should be permanently discontinued for the following:

- Any Grade 2 drug-related uveitis, eye pain, or blurred vision that does not respond to topical therapy and does not improve to Grade 1 severity within the re-treatment period OR requires systemic treatment.
- Any Grade 3 non-skin, drug-related AE lasting > 7 days or recurs, with the following exceptions for laboratory abnormalities, drug-related uveitis, pneumonitis, bronchospasm, neurologic toxicity, hypersensitivity reactions, infusion reactions, and endocrinopathies:
 - Grade 3 drug-related uveitis, pneumonitis, bronchospasm, neurologic toxicity, myocarditis, hypersensitivity reaction, or infusion reaction of any duration requires discontinuation.
 - Grade 3 drug-related endocrinopathies, adequately controlled with only physiologic hormone replacement do not require discontinuation. Adrenal insufficiency requires discontinuation regardless of control with hormone replacement.
 - Grade 3 drug-related laboratory abnormalities do not require treatment discontinuation except:
 - ◆ Grade 3 drug-related thrombocytopenia > 7 days or associated with bleeding requires discontinuation.
 - ◆ Grade ≥ 3 drug-related AST, ALT, or total bilirubin requires discontinuation (see below).
 - ◆ Concurrent AST or ALT > 3 \times ULN and total bilirubin > 2 \times ULN.

NOTE: In most cases of Grade 3 AST or ALT elevation, study treatment will be permanently discontinued. If the Investigator determines a possible favorable benefit-risk ratio that warrants continuation of study treatment, a discussion between the Investigator and the Medical Monitor/designee must occur.

- Any Grade 4 drug-related AE or laboratory abnormality (including, but not limited to, creatinine, AST, ALT, or total bilirubin), except for the following events which do not require discontinuation:
 - Grade 4 neutropenia ≤ 7 days.
 - Grade 4 lymphopenia or leukopenia or asymptomatic amylase or lipase elevation.
 - Isolated Grade 4 electrolyte imbalances/abnormalities that are not associated with clinical sequelae and are corrected with supplementation/appropriate management within 72 hours of their onset.

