 - Grade 4 drug-related endocrinopathy AEs, such as, hyper- or hypothyroidism, or glucose intolerance, which resolve or are adequately controlled with physiologic hormone replacement (corticosteroids, thyroid hormones) or glucose-controlling agents, respectively, may not require discontinuation after discussion with and approval from the Medical Monitor.

- Any event that leads to a dose omission lasting > 10 weeks from the previous dose requires discontinuation, with the following exceptions:
 - Dose omissions to allow for prolonged steroid tapers to manage drug-related AEs are allowed.
 - Dose omissions lasting > 10 weeks from the previous dose that occur for non-drug-related reasons may be allowed if approved by the Medical Monitor (or designee).
 - NOTE: Prior to re-initiating treatment in a participant with a dose omission lasting > 10 weeks, the Medical Monitor (or designee) must be consulted. Tumor assessments should continue per protocol, even if a dose is omitted. Periodic study visits to assess safety and laboratory studies should also continue Q4W or more frequently if clinically indicated during such dose omissions.
- Any AE, laboratory abnormality, or intercurrent illness which, in the judgment of the Investigator, presents a substantial clinical risk to the participant with continued nivolumab dosing.

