### 7.4.2 Modifications of Study Therapy

Participants are to start nivolumab within 3 calendar days of randomization. Participants will receive nivolumab at a dose of 480 mg as a 30-minute IV infusion for a maximum of 5 cycles (maximum 4 cycles for Arm B). Doses of nivolumab may be interrupted, omitted, or discontinued, depending on how well the participant tolerates the treatment. There will be no dose escalations or reductions of nivolumab allowed. For Q4W dosing cycles, participants may be dosed within a ± 3-day window. If a participant cannot receive nivolumab within a ± 3-day window, nivolumab must be omitted (skipped) for that cycle. If nivolumab is omitted, the other study medications may continue. If a participant discontinues nivolumab, the entire study treatment (CDK4/6 inhibitor

and anastrozole) must be discontinued. When nivolumab is scheduled to be administered on the same day with palbociclib plus anastrozole, nivolumab dosing should be started > 1 hour after palbociclib plus anastrozole ingestion. If nivolumab cannot be given within 3 days of palbociclib plus anastrozole administration for a given cycle, nivolumab must be omitted for that cycle. Participants who require a dose omission for nivolumab should be re-evaluated and resume treatment at the next cycle when re-treatment criteria are met.

Palbociclib can be interrupted, reduced, or discontinued both within a cycle and between cycles.

No dose modification for anastrozole is listed per full prescribing information.

Dose escalations (within subject) are not permitted for any study drugs.

Reason for dose modification will be retrieved from CRF dosing pages.

- The following parameters will be summarized by treatment group:
- Number of subjects with at least one dose modification (interrupted nivolumab dose, omitted nivolumab dose, interrupted palbociclib dose, reduced palbociclib dose).
- Number of nivolumab and/or palbociclib dose modifications per subject.
- Reason of nivolumab and/or palbociclib dose modification.

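### Nivolumab relative dose intensity ignores cycles omitted after the last (or before the first) nivolumab dose, so an affected participant shows 100% instead of 80%, 75% or 60%

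*SAP*

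**What the plan says.** SAP Table 7.4.1-1, which covers nivolumab only, gives the schedule as "480 mg every 4 weeks". It defines RDI as cumulative dose divided by (window in days × 480/28), times 100, where the window is "Last dose date} - \text{Start dose date} + 28". SAP 7.4.1 reports the result by study therapy and treatment group: "Relative dose intensity (%) using the following categories: < 50%; 50 - < 70%; 70 - < 90%; 90 - < 110%; ≥ 110" percent.

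Nivolumab is given "for a maximum of 5 cycles (maximum 4 cycles for Arm B" (SAP 7.4.2; same rule in Protocol 7.1.1). If it cannot be given within ±3 days, "nivolumab must be omitted (skipped) for that cycle", and "If nivolumab is omitted, the other study medications may continue". Nivolumab dose reduction is not allowed. Protocol 9.2.9 adds that a delay in the management algorithms is to be read as an omission.

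Two rules in Protocol 8.1.1 limit how long nivolumab can be missed while other drugs go on. First: "If a participant discontinues nivolumab, the entire study treatment (CDK4/6 inhibitor and anastrozole) must be discontinued". Second: "Any event that leads to a dose omission lasting > 10 weeks from the previous dose requires discontinuation", with exceptions for prolonged steroid tapers and, if approved, for reasons unrelated to the drug.

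Other exposure summaries are planned. SAP 7.4.1 has number of doses received, cumulative dose and a by-subject dosing listing. SAP 7.4.2 has participants with an omitted nivolumab dose, modifications per participant, and reasons.

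**The concern.** A window from first to last dose works when a late dose is delayed, because the delay lies between two doses and lengthens the denominator. Here a late dose is lost for that cycle, and nivolumab cannot be reduced. Skipped cycles are therefore the main way nivolumab is under-delivered while treatment continues. The SAP formula sees a skipped cycle only if nivolumab has been given before it and is given again after it.

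The situation is foreseeable. Protocol 7.4.4.1 calls for omission for Grade 2 non-skin drug-related events other than fatigue, and Protocol 7.4.4.2 generally requires recovery to Grade 1 or baseline before resuming. With at most five doses (four in Arm B), an event in Cycle 3 or 4 can use up the rest of the course. In Arm B, an event during the first palbociclib and anastrozole cycle can lead to omission of the first scheduled nivolumab dose in Cycle 2.

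At stake is whether the RDI table describes delivery correctly. Two participants with the same number of doses and the same time on treatment can fall in different categories only because of where the skip occurred.

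**Working it through.** **Inputs.** 480 mg per 28 days and the window formula (SAP Table 7.4.1-1); five scheduled doses in the run-in and Arm A, four in Arm B (SAP 7.4.2); reporting categories (SAP 7.4.1). Assumption: cycles run on schedule, with Day 1 of Cycles 1 to 5 on days 1, 29, 57, 85 and 113, and the other drugs continue into Cycle 5.

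**Formula.** RDI = cumulative dose / [(last − first + 28) × 480/28] × 100. The documents give no numeric RDI to reproduce, so full delivery serves as the check. Arm A: 2400 / [(112 + 28) × 480/28] = 2400/2400 = 100%. Arm B: 1920 / [(84 + 28) × 480/28] = 1920/1920 = 100%.

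**Which last dose?** If the last dose date meant the last dose of any study drug (day 140), full delivery in Arm A would give 2400 / [(139 + 28) × 480/28] = 83.8%. The +28 works only with the last nivolumab dose.

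**Scenarios.** The last column divides by 480 mg × scheduled nivolumab cycles started.

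| Arm, cycles skipped | Cumulative mg | Window, days | SAP denominator, mg | SAP RDI | RDI on cycles started |
|---|---|---|---|---|---|
| A, C4 | 1920 | 112 + 28 = 140 | 2400 | 80% | 1920/2400 = 80% |
| A, C5 | 1920 | 84 + 28 = 112 | 1920 | **100%** | 1920/2400 = 80% |
| A, C3 and C4 | 1440 | 140 | 2400 | 60% | 1440/2400 = 60% |
| A, C4 and C5 | 1440 | 56 + 28 = 84 | 1440 | **100%** | 1440/2400 = 60% |
| B, C4 | 1440 | 84 + 28 = 112 | 1920 | 75% | 1440/1920 = 75% |
| B, C5 | 1440 | 56 + 28 = 84 | 1440 | **100%** | 1440/1920 = 75% |
| B, C2 | 1440 | 56 + 28 = 84 | 1440 | **100%** | 1440/1920 = 75% |

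Mid-course skips agree under both definitions. Skips at either end do not: participants who belong in 70 to <90% (80%, 75%) or 50 to <70% (60%) appear in 90 to <110%. The ±3-day window cannot explain this. Moving the last of five doses by 3 days changes full-delivery RDI only to 2400 / (143 × 480/28) = 97.9% or 2400 / (137 × 480/28) = 102.2%.

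**The 10-week limit.** After a last dose in Cycle 3 (day 57), Cycles 4 and 5 fall due 4 and 8 weeks later. Ten weeks is day 57 + 70 = 127, two weeks into Cycle 5. Two trailing skips can therefore occur before the limit is reached, and Cycle 5 has already been started. A third (last dose in Cycle 2, Cycle 5 due 12 weeks later) needs one of the exceptions.

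**Scale at arm level.** With 40 participants planned per nivolumab arm, each affected participant raises the arm mean RDI by 20/40 = 0.5 points (Arm A, one skip), 40/40 = 1.0 point (Arm A, two skips) or 25/40 = 0.6 points (Arm B, one skip).

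**The case against.** The strongest reply is that this is a convention rather than a mistake. Ending the window at a drug's own last dose is usual, and Table 7.4.1-2 does the same for anastrozole and palbociclib. Palbociclib may be stopped while nivolumab and anastrozole continue (Protocol 8.1.3), so its RDI misses trailing cycles too. Changing nivolumab alone would put the drugs on different bases. This stands as a reason to align or footnote both tables. It does not rescue the nivolumab formula, which does count skipped cycles mid-course and so treats equal delivery unequally.

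Second, delivery is visible elsewhere: with at most five doses, a count of three in Arm A plainly shows the shortfall. This stands and limits the consequence. None of the other summaries, however, expresses dose given as a percentage of dose scheduled, and a 90 to <110% entry would sit awkwardly beside them.

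Third, the trigger is narrow. Discontinuing nivolumab ends all study treatment, the 10-week rule caps most omissions, and no omission frequency is given. All of this stands.

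Fourth, counting cycles started does not measure delivery of the whole planned course: a participant who stops everything after two cycles with both doses given still shows 960/960 = 100%. This is correct, and the revised definition should say what it measures.

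**Conclusion.** The point holds as an error per participant in a descriptive exposure summary. When nivolumab cycles are skipped after the last nivolumab dose while other study drugs continue, RDI reads 100% instead of 80% or 60% in Arm A (one or two skips) or 75% in Arm B (one skip), and the participant is placed one or two categories too high. A skipped first scheduled dose has the same effect, less often. Skips at the ends of the course can only raise RDI. The figures assume on-schedule 28-day cycles and treatment continuing into Cycle 5.

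Three stronger readings are tempting and are not supported:

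- **Delivery in the nivolumab arms is materially overstated.** The documents give no frequency of trailing or leading omissions, so only the effect per affected participant can be computed.
- **A low RCB 0-I rate would be misread as inactivity.** The primary analysis estimates RCB 0-I in all randomized participants as randomized (SAP 7.5.1), no planned efficacy analysis shown in the SAP uses RDI, and doses received, cumulative dose and omissions are reported separately.
- **Arm A participants could commonly receive Arm B's nivolumab schedule and still show 100%.** Skipping only Cycle 1 in Arm A does give 1920/1920 = 100%. It is an edge case: nivolumab is to start within 3 days of randomization, and most omission criteria require a drug-related event.

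**What to change.** In SAP Table 7.4.1-1, define nivolumab RDI as cumulative dose (mg) / (480 mg × number of cycles the participant started on any study drug in which nivolumab was scheduled) × 100. Count from Cycle 1 in the run-in and Arm A, and from Cycle 2 in Arm B. State that it measures delivery while on study treatment, not delivery of the full planned course.

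In Table 7.4.1-2, either put the oral-drug RDI on the same basis or add a footnote that its denominator ends at each drug's own last dose.

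The cost is a change to one table cell, a footnote and a small programming change. The SAP already records dose and dosing date for every study drug; if cycle number is not held directly, cycles started must be derived from those dates. Full delivery stays at 100%, and mid-course skips keep their values apart from the small ±3-day effects. Reported nivolumab RDI will be slightly less favourable if end-of-course omissions occur, and until Table 7.4.1-2 is aligned the nivolumab and oral-drug figures will rest on different bases. No dosing rule or data collection changes.
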